10.6 FUTURE USE OF STORED SPECIMENS AND DATA

Research samples collected from participants consenting to this protocol will be stored in locked secure freezers belonging to NIDCR and NIAMS. The freezers are located in Building 10 and Building 50 at the NIH. Only study investigators and participating research personnel will have access to the samples. Samples will be kept indefinitely unless there is a significant justification for destroying them. The Principal Investigator will report the loss or destruction of samples collected under this protocol to the Institutional Review Board (IRB).

Abbreviated Title: Tofacitinib in Sjögren's syndrome

Version Date: 07/01/2024

All samples will be coded and will not have personal identifiers. The codes for identifiers will be contained in a secure electronic database (CTDB) and a participant code log that is maintained in secure research files. An electronic record log with identifiers of all collected research specimens will be kept. These will be stored in secure NIH computers.

Coded samples may be shared with collaborators within and outside the NIH. Any remaining samples will be stored in the NIDCR or NIAMS locked freezers. Stored samples may be used for studies related to SS or other autoimmune or disorders affecting salivary glands. Approval from the IRB will be obtained prior to any research use of stored samples beyond the scope of this study.

All participant samples will be coded and used for research purposes without sharing identifying information and all collaborators will follow federal rules for clinical research.

10.7 SAFETY OVERSIGHT

In addition to the PI's responsibility for oversight, this study will be monitored by the NIDCR Division of Intramural Research Data and Safety Monitoring Committee (DSMC). The DSMC will include members with expertise in a broad range of areas, including, but not limited to, human subjects' protection, clinical trial implementation, biostatistics, rheumatology, and medical bone and mineral metabolism. The DSMC will meet periodically to assess safety and efficacy data (if applicable), study progress, and data integrity for the study. The DSMC will determine frequency of review at the first meeting, but typically will meet at least once a year. The DSMC may also choose to electronically review periodic data and safety reports in addition to convening data review meetings. If safety concerns arise, more frequent meetings may be held. In addition, unscheduled meetings can be requested by any party with responsibility of overseeing the study. The DSMC will provide recommendations to the NIDCR concerning the continuation, modification, or termination of the trial. The DSMC will operate under the rules of an NIDCR-approved charter. The roles and responsibilities of committee members and meeting procedures will be formally described in the charter.

The DSMC will provide its input to the National Institute of Dental and Craniofacial Research, Clinical Director and the PI.

The DSMC will be alerted if any of the following situations occur:

- An unexpected fatal or life-threatening event assessed as related to the use of study drug.
- Three or more participants with similar severe AEs (Grade 3 or 4) assessed as related to the use of study drug.

The Principal Investigator will be responsible for monitoring the accruing safety data related to suspension guidelines and for alerting the DSMC chair when a criterion is met. The DSMC chair, through the DSMC Executive Secretary, will be alerted by email within 7 calendar days of determination that a criterion has been met. The DSMC will issue a recommendation on study continuation to the NIDCR Clinical Director or designee after reviewing data related to the suspension guideline. If the study is stopped, participants will receive conventional care for any study-related AEs and continue to be followed for clinical and safety outcomes. Otherwise, the study will continue per the DSMC recommendations. The Principal Investigator and the Clinical Director will provide the recommendations of the DSMC to the IRB.

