2.4 RISK/BENEFIT ASSESSMENT

2.4.1 Risks/discomforts associated with Tofacitinib

Tofacitinib is approved by the Food and Drug Administration (FDA) for treatment of rheumatoid arthritis, psoriatic arthritis and ulcerative colitis. However, on September 1, 2021, based on a completed review of a large, randomized safety clinical trial, the FDA concluded that there is an increased risk of serious heart-related events such as heart attack or stroke, cancer, blood clots, and death with the arthritis and ulcerative colitis medicines Tofacitinib. This lead to the requirement of a “**Boxed Warning**” as follows:

Boxed Warning

WARNING: SERIOUS INFECTIONS, MORTALITY, MALIGNANCY, MAJOR ADVERSE CARDIOVASCULAR EVENTS (MACE), AND THROMBOSIS

Increased risk of serious bacterial, fungal, viral, and opportunistic infections leading to hospitalization or death, including tuberculosis (TB).

Higher rate of all-cause mortality, including sudden cardiovascular death with Tofacitinib vs. TNF blockers in rheumatoid arthritis (RA) patients.

Malignancies have occurred in patients treated with Tofacitinib. Higher rate of lymphomas and lung cancers with Tofacitinib vs. TNF blockers in RA patients.

Higher rate of MACE (defined as cardiovascular death, myocardial infarction, and stroke) with Tofacitinib vs. TNF blockers in RA patients.

Thrombosis has occurred in patients treated with Tofacitinib. Increased incidence of pulmonary embolism, venous and arterial thrombosis with Tofacitinib vs. TNF blockers in RA patients.

Abbreviated Title: Tofacitinib in Sjögren's syndrome

Version Date: 07/01/2024

Notwithstanding, tofacitinib is generally well-tolerated in individuals with Rheumatoid Arthritis. The data on adverse events associated with exposure to Tofacitinib are gathered from two Phase II and 5 Phase III multi-center, double-blind, placebo controlled clinical trials where participants were randomized to Tofacitinib 5 mg twice daily, 10 mg twice daily or placebo, with or without concomitant disease modifying drugs (DMARDs); most commonly methotrexate. Adverse events associated with Tofacitinib included the following:

Infections

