However, it is noteworthy that Sjögren's syndrome patients have an increased risk of lymphoma development⁵⁸. This is exemplified in a focused case-matched control analysis by Mariette et al., examining the incidence rates (IR; events per 100 patient-years) and standardized incidence ratios (SIRS) with respect to risk of lymphoma⁵⁶. Among 19 Tofacitinib studies (Phase I [n=2], Phase II [n=9], Phase III [n=6], and long-term extension [n=2]) in patients with moderate-to-severe rheumatoid arthritis, there were 19 lymphomas in 19,406 patient-years of exposure (IR = 0.10) and the SIR was 2.656. More patients with lymphomas had a history of Sjögren's syndrome in the context of rheumatoid arthritis and were commonly positive for Anti-cyclic citrullinated peptide (anti-CCP). These results indicate that there are minimal differences in lymphoma risk for Tofacitinib across all doses and that the increased risk reported likely reflects the background disease-specific risk attributable to Sjögren's syndrome. However, we acknowledge that we do not yet know the risk of Tofacitinib administration on lymphomagenesis in Sjögren's syndrome patients.

Thus, very close clinical follow up in this patient cohort for any changes in patient status is essential and will be provided to participants.

Thrombosis:

Thrombosis, including pulmonary embolism (PE), deep venous thrombosis (DVT), and arterial thrombosis, have occurred in patients treated with Tofacitinib and other Janus kinase (JAK) inhibitors used to treat inflammatory conditions. Many of these events were serious and some resulted in death.

Patients with rheumatoid arthritis 50 years of age and older with at least one cardiovascular risk factor treated with Tofacitinib at both 5 mg or 10 mg twice daily compared to TNF blockers in RA Safety Study 1 had an observed increase in incidence of these events. The incidence rate of DVT per 100 patient-years was 0.22 for Tofacitinib 5 mg twice a day, 0.28 for Tofacitinib 10 mg twice a day, and 0.16 for TNF blockers. The incidence rate of PE per 100 patient-years was 0.18 for Tofacitinib 5 mg twice a day, 0.49 for Tofacitinib 10 mg twice a day, and 0.05 for TNF blockers.

In a long-term extension study in patients with UC, five cases of pulmonary embolism were reported in patients taking Tofacitinib 10 mg twice daily, including one death in a patient with advanced cancer.

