8.7.3 Expectedness

For reporting purposes, the medically responsible investigator will be responsible for determining whether an adverse event (AE) is expected or unexpected. An AE will be considered unexpected if the nature, severity, or frequency of the event is not consistent with the risk information previously described for the study intervention.

Unexpected adverse events are those not listed in the Package Insert (P.I.) or Physicians’ Desk Reference (PDR), published medical literature, protocol, informed consent document or not identified. This includes adverse events for which the specificity or severity is not consistent with the description in the P.I. or PDR. For example, under this definition, hepatic necrosis would be unexpected if the P.I. or I.B. only referred to elevated hepatic enzymes or hepatitis.

For consistency of labeling and categorizing adverse events, the National Cancer Institute (NCI) Common Terminology Criteria for Adverse Events (CTCAE), Version 5.0 will be used in this study.

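### A single drug-related death from a risk already listed as potentially fatal, if classed as expected, triggers no mandatory 7-day alert to the DSMC

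*Combined protocol and SAP*

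**What the plan says.** Section 10.7 (Safety Oversight) lists two events that require the DSMC to be alerted. The first concerns a single event: "An unexpected fatal or life-threatening event assessed as related to the use of study drug". The second is a cluster rule, which counts affected people across the trial: "Three or more participants with similar severe AEs (Grade 3 or 4) assessed as related to the use of study drug".

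The deadline depends on these criteria: the DSMC chair "will be alerted by email within 7 calendar days of determination that a criterion has been met". After an alert the DSMC reviews the data and recommends whether the study should continue.

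Section 8.7.3 (Expectedness) says that "the medically responsible investigator will be responsible for determining whether an adverse event (AE) is expected or unexpected". The references for that decision are the package insert or PDR, the published literature, the protocol and the consent document. An event is also "unexpected if the nature, severity, or frequency of the event is not consistent with the risk information previously described".

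Section 2.4.1 puts fatal outcomes among the known risks. The boxed warning covers serious infections that can be fatal, and also "Higher rate of all-cause mortality, including sudden cardiovascular death with Tofacitinib vs. TNF blockers". On thrombosis the section adds: "Many of these events were serious and some resulted in death".

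Section 8.8.1 sends SAEs to the IRB, the NIDCR Clinical Director's Office (7 calendar days) and the drug supplier (24 hours, or at once if fatal or life-threatening). The DSMC is not on that list.

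**The concern.** The first criterion has three conditions: fatal or life-threatening, related, and unexpected. For this drug the most plausible related deaths are of kinds the protocol has already described, so the third condition can exclude them. Whether the independent committee must be told then depends on a classification made inside the study team.

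The second criterion is a cluster rule. It needs three similar cases and stops at Grade 4, whereas the toxicity definition in the Synopsis and in section 3 is Grade 3 or higher.

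Safety is the primary endpoint, and the DSMC is the body that recommends on continuation. Section 2.4.1 also says there are no data on the drug in Sjögren's syndrome, so a death that would be expected in RA is still new information here.

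**Working it through.** **Logic of the rule.** The plan attaches no operating characteristic to these criteria, so there is no stated figure to reproduce. As written:

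alert = [(fatal or life-threatening) AND unexpected AND related] OR [at least 3 participants with similar related Grade 3 or 4 events]

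| Related event(s) | Criterion 1 | Criterion 2 | Alert required |
|---|---|---|---|
| One death, classed unexpected | met | not met | yes |
| One death, classed expected | not met | not met (1 < 3) | no |
| Two deaths, both classed expected | not met | not met (2 < 3) | no |
| One or two life-threatening events, classed expected | not met | not met | no |
| Three similar Grade 4 events, classed expected | not met | met | yes |

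The second row does not depend on how death is graded, because one event cannot satisfy a three-participant rule. If death is Grade 5 on the CTCAE scale (an assumption, since the protocol does not spell out the grades), a fatal case never counts toward criterion 2 at all.

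**Other routes to the DSMC in the text.**
- Section 8.8.1: the DSMC is not an SAE recipient.
- Sections 8.8.4 and 8.8.5: unanticipated problems must also be unexpected, and they go to the IRB.
- Section 10.7: routine meetings are typically at least yearly, against a 168-day treatment period. Extra or unscheduled meetings are optional and have no deadline.

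**Can the cluster rule stand in for a single-event rule?** Inputs: 20 participants on tofacitinib for 168 days (section 4.1); 5 mg rates of 0.91 (MACE) and 0.18 (PE) per 100 patient-years (section 2.4.1). Event counts are taken as Poisson.

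- Exposure: 20 × 168 / 365.25 = 9.20 patient-years.
- MACE: mean = 9.20 × 0.0091 = 0.0837. P(≥1) = 1 − exp(−0.0837) = 8.0%. P(≥3) = 0.0092%. P(≥3 given ≥1) = 0.0092 / 8.03 = 0.11%.
- PE: mean = 9.20 × 0.0018 = 0.0166. P(≥1) = 1.6%. P(≥3) = 0.000075%.

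Upper bound on exposure: if all 11 replacements are used, 41 × 2/3 ≈ 27 are on drug. With full treatment that is 27 × 168 / 365.25 = 12.42 patient-years and a MACE mean of 0.113. Then P(≥1) = 10.7%, P(≥3) = 0.022%, and P(≥3 given ≥1) = 0.21%. If instead the seven additional tofacitinib slots reflect withdrawals by day 56 (one replacement rule in section 7.2), exposure is at most about 20 × 168 + 7 × 56 = 3,752 days = 10.3 patient-years, and P(≥1) is 8.9%.

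Binomial check with 20 participants at assumed per-participant risks:

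| Assumed risk | P(≥1) | P(≥3) |
|---|---|---|
| 1% | 18.2% | 0.1% |
| 2% | 33.2% | 0.7% |
| 5% | 64.2% | 7.5% |

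At low rates, three cases will almost never accrue even when one occurs.

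**The case against.** The strongest reply has four parts.

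1. **Expectedness is constrained.** Section 8.7.3 says an event whose severity or frequency goes beyond the described risk is unexpected. A death from a risk described without a fatal outcome should therefore trigger the alert. Even for listed fatal risks, the data come from RA and this trial excludes many at-risk people, so an investigator has grounds to call such a death unexpected. This stands as a limit: the gap covers only risks whose listed outcomes include death. Within those, the text permits the expected classification, and the decision rests on one person's judgement.

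2. **The death is not hidden.** The Clinical Director's Office hears of every SAE within 7 calendar days, and the Clinical Director also receives the DSMC's advice. Anyone with oversight responsibility can request an unscheduled DSMC meeting, and section 10.2 allows suspension for unacceptable risk. All true, but no text requires anyone to tell the DSMC promptly.

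3. **The charter is not in the documents** and may contain a stricter duty. That cannot be excluded, so the finding is about the protocol text.

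4. **The rates measure something broader.** They count all MACE and PE, fatal or not and related or not, in RA patients aged 50 or older with a cardiovascular risk factor. This also stands. They show how a count-of-three rule behaves when events are rare; they do not predict deaths in this trial.

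It can also be said that extending criterion 2 is redundant once criterion 1 is widened. It is not wholly so: a death followed by two similar Grade 3 events would otherwise never count as a cluster of three.

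**Conclusion.** The concern holds. As the protocol is written, one related death, or even two, from a cause whose fatal outcome is already listed requires no 7-day DSMC alert if classed as expected. The same applies to a first or second expected life-threatening event. What is missing is the automatic prompt alert to the DSMC, not all oversight.

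The logical gap rests on no numerical assumption. The numbers show only that the cluster rule is no substitute: at the protocol's MACE rate, if any event occurs, the chance that three do is about 0.1% with 20 participants, and about 0.2% at the upper bound of 27 with full exposure. The rate in Sjögren's syndrome is unknown and may be lower. The change is worth making, with the caveat that the charter may already cover the point.

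**What to change.** Make two edits in section 10.7:

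- In the first criterion, delete the word unexpected and state that it applies whether or not the event is expected. Keep the requirement that the event be assessed as related.
- In the second criterion, replace Grade 3 or 4 with Grade 3 or higher, in line with the toxicity definition in the Synopsis and section 3.

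The 7-day email route stays as it is. Neither edit touches dosing, treatment stopping or any other clinical rule.

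The cost is two wording changes plus the alerts they generate. Each alert also calls for DSMC review and a recommendation on continuation, so it is more than an email. The number should be small: at most 41 participants are randomized (30 + 11), and the MACE illustration gives an expected count of only 0.08 events on tofacitinib. If the charter already requires such alerts, 10.7 should be brought into line with it.

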10.8 CLINICAL MONITORING

Clinical site monitoring is conducted to ensure that the rights of human subjects are protected, that the study is implemented in accordance with the protocol and/or other operating procedures, and that the quality and integrity of study data and data collection methods are maintained. Monitoring for this study will be performed by the NIDCR Clinical Research Operations and Management Support (CROMS) contractor. The monitor will evaluate study processes and documentation based on the International Council for Harmonization (ICH), E6: Good Clinical Practice guidelines (GCP).

Details of clinical site monitoring will be documented in a Clinical Monitoring Plan (CMP). The CMP will specify the frequency of monitoring, monitoring procedures, the level of clinical site monitoring activities (e.g., the percentage of participant data to be reviewed), and the distribution of monitoring reports. Some monitoring activities may be performed remotely, while others will take place at the study site(s). Staff from the NIDCR CROMS contractor will conduct monitoring activities and provide reports of the findings and associated action items in accordance with the details described in the CMP. Documentation of monitoring activities and findings will be provided to the study PI, NIDCR-OCTOM, and NIDCR Office of the Clinical Director (OCD) staff.

10.9 QUALITY ASSURANCE AND QUALITY CONTROL

Internal quality assurance activities will include study team meetings, where the protocol team will review any new consents, unanticipated problems, and adverse events, and quarterly reporting of quality assurance/quality improvement activities to the NIDCR Office of the Clinical Director Clinical Operations Manager and NIDCR-OCTOM.

The study team will perform internal quality management of study conduct, data and biological specimen collection, documentation and completion.

Quality control (QC) procedures will be implemented beginning with the data entry system and data QC checks that will be run on the database will be generated. Any missing data or data anomalies will be communicated to the site(s) for clarification/resolution.

The data will be further validated via a series of manual edit checks, and all relevant data queries will be raised and resolved on an ongoing basis. Complete, clean data will be frozen to prevent further inadvertent modifications. All discrepancies will be reviewed and any resulting queries will be resolved with the investigators and amended in the database. All elements of data entry (i.e., time, date, verbatim text, and the person performing the data entry) will be recorded in an electronic audit trail to allow all data changes in the database to be monitored and maintained in accordance with federal regulations.

10.10 DATA HANDLING AND RECORD KEEPING

10.10.1 Data Collection and Management Responsibilities

Data collection is the responsibility of the clinical trial staff at the site under the supervision of the site investigator. The investigator is responsible for ensuring the accuracy, completeness, legibility, and timeliness of the data reported.

All source documents should be completed in a neat, legible manner to ensure accurate interpretation of data.

Abbreviated Title: Tofacitinib in Sjögren's syndrome

Version Date: 07/01/2024

Hardcopies of the study visit worksheets will be provided for use as source document worksheets for recording data for each participant enrolled in the study. Data recorded in the electronic case report form (eCRF) derived from source documents should be consistent with the data recorded on the source documents.

Clinical data (including adverse events (AEs), concomitant medications, and expected adverse reactions data) and clinical laboratory data will be entered into Clinical Trials Data Base (CTDB), a 21 CFR Part 11-compliant data capture system provided by the Research Nurse Coordinator. The data system includes password protection and internal quality checks, such as automatic range checks, to identify data that appear inconsistent, incomplete, or inaccurate. Clinical data will be entered directly from the source documents.

Study staff will complete electronic case report forms (eCRFs) via a web-based electronic data capture (EDC) system (Clinical Trials Database, CTDB) that is compliant with Part 11 Title 21 of the Code of Federal Regulations. Participant electronic medical records in the Clinical Research Information System (CRIS) will be used as source documents for these eCRFs.

Participants will also complete periodic questionnaires as outlined in the study procedures through the Clinical Trial Survey System (CTSS) – an ancillary web-based application associated with CTDB. These participant-completed questionnaires in CTSS will be used as source documents for the study. The CTSS is accessible outside the NIH and allows participants to remotely respond to clinical questionnaires with secure passwords administered by CTDB. Security of the database system is maintained through an application firewall, military grade encryption and SSL certificates, removal of personal identifiers consistent with HIPAA requirements (45 C.F.R.164.514(a),(b)&(c)), and the incorporation of audit trails. The servers are physically located in a secured NIH data center with controlled limited access. If for any reason, the CTSS system is unavailable for use by a participant, questionnaires may be completed in paper form. The paper form will be used as the source. Study team member(s) will enter data into the CTDB database.

Paper-based CRFs and physician assessments may be completed in addition to completion of web-based CRFs. Completed paper-based forms will be imputed into appropriate CTDB database. CRFs, participant questionnaire data will be kept in the CTDB database.

Research records and all source documents will be kept in locked cabinets or rooms, and computer research databases will be stored in a secure, password-protected environment, per standard NIH policies. Only study investigators and participating research personnel will have access to the data.

In the future, other investigators (at the NIH) may wish to study these samples and/or data. In that case, IRB approval must be sought prior to any sharing of samples. Any clinical information shared about the sample without participant identifiers would similarly require prior IRB approval.

The research use of stored, unlinked or unidentified samples may be exempt from the need for prospective IRB review and approval. Exemption requests will be submitted in writing to the NIH Office of Human Participants Research, which is authorized to determine whether a research activity is exempt.

